10.3.3. Binocular Diplopia

All participants will be assessed for presence of binocular diplopia with correction at Screening/Baseline and all visits on and after the 3-months postoperatively (except Enhancement Month 1 and IOP confirmation). It will be documented as “present” or “absent”.

10.3.4. External Ocular Examination (Exophthalmometry)

Participants will be assessed for proptosis at the Screening/Baseline, Month 1, Month 3 and Month 12 Visits. If proptosis is grossly present, a Hertel exophthalmometer should be used to measure the amount of proptosis.

10.3.5. Specular Microscopy

Three quality central corneal images of the study eye should be taken by Specular Microscopy at Screening/Baseline, Year-1, and Year-5 visits prior to any administration of drops or contact with the eyes. Central corneal thickness (CCT) and cell density (CD) will be obtained and the values will be recorded from each image. The average will be calculated for each variable.

10.3.6. Biomicroscopy

A slit lamp examination will be performed on the lids, conjunctiva, cornea, anterior chamber, iris, and lens at each visit (except surgery, enhancement, and IOP confirmation visits). Any abnormalities will be graded as clinically significant or not and severity graded as mild (=1), moderate (=2), or severe (=3). Cells will be graded as trace (1-5 cells), mild (6-15 cells), or moderate/severe (> 15 cells / High Powered Field). The study tube position will be examined in two places: (1) tube measured approximately 1mm in from the limbus, and (2) the tube tip in the anterior chamber (AC), and will be assessed as:

- (a) Touching cornea
- (b) Close to cornea
- (c) Mid-AC
- (d) Close to iris, or

(e) Touching iris.

If the study tube is present and visible in the AC, the length of the tube will be measured with the slit beam in millimeters. If the tube is behind the iris, document whether the tube is tenting the iris. The initial AS tube will be measured in the same fashion as the study tube at the Screening/Baseline, Year-1, Year-3, and Year-5 Visits.

If there is no view beyond the cornea, "inadequate view" will be marked on the data collection form.

10.3.7. Intraocular Pressure

IOP measurements should be performed at all study visits at approximately the same time of day from the Screening/Baseline visit. All IOP checks must be performed prior to dilation.

Two individuals (an operator and a masked reader) must perform the IOP measurements. The operator will be responsible for operating the instrument while the masked reader will read and record the results. In order to minimize the measurement variation, all IOP measurements for any individual participant should preferably be performed by the same operator with the same tonometer.

Starting with the right eye, alternating between the two eyes, two IOP measurements should be performed on each eye. The mean of the two measurements will be used for analysis. If the difference between the two measurements for an eye is greater than 2 mm Hg, a third measurement must be taken. The median of the three measurements will be used for analysis.

Three instruments for measuring IOP are allowed and will be chosen based on the participant's cornea status. The same type of instrument should be used for the duration of the study unless new pathology has developed that prevents accurate usage of the initial method.

Goldmann Applanation Tonometry: Following instillation of a drop of fluorescein and anesthetic, ensure the participant's head is properly positioned in the chin rest and against the forehead rest; encourage the participant to continue breathing normally. The operator will look through the slit-lamp and adjust the dial while the masked reader records the IOP measurement. The reader will be masked to the participant's treatment.

Pneumotonometry: A pneumotonometer will be used in cases of corneal edema, corneal scarring, or irregular corneal astigmatism. The technique described in the user's manual should be performed. The operator will turn the display facing away from himself/herself while the masked reader records the measurements.

Tono-Pen: The Tono-Pen will be used in cases of corneal edema, corneal scarring, or irregular corneal astigmatism at sites where a pneumotonometer is not available. The

technique described in the user's manual should be performed. The operator will hold the display out to the reader for the IOP and reliability to be recorded.

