7.3. Masking

Since intraocular pressure (IOP) is one of the most important measurements for determining treatment success or failure, every effort will be made to obtain unbiased measurements through a masking procedure. IOP will be performed by two study personnel, an operator and a masked reader. Masking procedures are detailed in section 10.3.7.

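### For Goldmann tonometry the plan masks the reader but neither masks the operator who sets the value nor keeps the reading from that operator, so the IOP part of the primary outcome is only partly protected from operator bias

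*Combined protocol and SAP*

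**What the plan says.** Section 7.3 (Masking) treats IOP as a key measurement for judging success or failure and states that "every effort will be made to obtain unbiased measurements through a masking procedure". The procedure it describes is a pair: "IOP will be performed by two study personnel, an operator and a masked reader". Section 10.3.7 divides the work in the same way for all instruments: "The operator will be responsible for operating the instrument while the masked reader will read and record the results".

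The three instruments are then described in turn:

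- **Goldmann:** "The operator will look through the slit-lamp and adjust the dial while the masked reader records the IOP measurement". The next sentence adds: "The reader will be masked to the participant's treatment". Nothing is said about masking the operator.
- **Pneumotonometer**, for corneal edema, scarring or irregular astigmatism: "The operator will turn the display facing away from himself/herself while the masked reader records the measurements".
- **Tono-Pen**, for the same corneas where no pneumotonometer is available: "The operator will hold the display out to the reader for the IOP and reliability to be recorded".

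Two readings are taken per eye, alternating between eyes. A third is taken if the two differ by more than 2 mmHg, and the median is then used. Readings for one participant "should preferably be performed by the same operator with the same tonometer". Table 2 schedules IOP in both eyes at Screening/Baseline and in the study eye only at every later visit, including the confirmation visit.

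**The concern.** With Goldmann tonometry the value is produced by the operator, who judges the endpoint and turns a graduated dial. The reader then reads what has been set. Masking the reader prevents biased reading and recording. It cannot prevent biased setting if the operator knows both the arm and the number.

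Knowledge of the arm is realistic. Section 10.3.6 has the study tube examined at the slit lamp and measured when it is visible in the anterior chamber, and Goldmann readings are taken through the slit lamp. Masking the operator to the arm may therefore not be feasible, and keeping the number from the operator becomes the practical safeguard. The plan writes that safeguard for the pneumotonometer and omits it for the instrument used in all other corneas.

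At stake are cut points. IOP above 18 mmHg, or a reduction of less than 20%, on maximum tolerated topical medication counts towards failure (section 4.1). A small, unintended shift moves borderline eyes across such a line. A consistent shift by the same operator can recur at the confirmation visit.

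**Working it through.** **1. The instrument texts side by side (section 10.3.7)**

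| | Goldmann | Pneumotonometer | Tono-Pen |
|---|---|---|---|
| When used | Unless the cornea prevents it | Edema, scarring, irregular astigmatism | Same, if no pneumotonometer |
| Operator stated to be masked to the arm | No | No | No |
| Reading kept from the operator | Not stated | Display turned away | Display held out to the reader |
| Does the operator's hand set the value? | Yes, by the dial | No dial described | No dial described |

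The operator is not masked to the arm with any instrument. The instruments differ in whether the reading is explicitly kept from the operator. On that point the Goldmann text is the least explicit, and Goldmann is the only one of the three for which the operator is described as adjusting a dial.

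**2. Dial position between readings**

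Section 10.3.7 alternates right and left eyes, so a fellow-eye reading would move the dial between the two readings of the study eye. Table 2, however, lists the study eye only after baseline. If sites follow Table 2, nothing intervenes at the visits that decide failure, and no sentence requires a reset. The second reading may then start where the first ended, and agreement within 2 mmHg could partly reflect the starting position. If sites alternate eyes at follow-up as well, this does not arise.

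**3. Illustration of size (all inputs assumed)**

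The plan gives no figure for operator bias or for the follow-up IOP distribution, so it has no figure of its own to reproduce here. Assume that follow-up IOP is normal with mean 15 and SD 4 mmHg, and that readings in one arm are shifted upwards by d.

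P(IOP > 18) = 1 − Φ((18 − 15 − d)/4)

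- d = 0: 1 − Φ(0.750) = 22.7%
- d = 0.5: 1 − Φ(0.625) = 26.6%, an increase of 3.9 points
- d = 1: 1 − Φ(0.500) = 30.9%, an increase of 8.2 points

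Across means of 14 to 16 and SDs of 3 to 5 mmHg, the increase is 3.0 to 5.6 points for d = 0.5 and 6.2 to 11.7 points for d = 1.

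**4. Effect of confirmation**

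Now require two readings above 18 mmHg at mean 15 and SD 4, with the same shift both times and an assumed between-visit correlation of 0.3 to 0.7 (bivariate normal). The increase falls to 2.4 to 3.0 points for d = 0.5 and to 5.3 to 6.5 points for d = 1. Confirmation reduces a repeated shift but does not remove it. The criterion of less than 20% reduction was not modelled.

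**The case against.** The strongest reply is that the plan already does a good deal. Every measurement needs two people. The masked reader reads as well as records, which is more than transcription. A Goldmann operator looking through the slit lamp may well not see the dial. Readings are replicated, and an IOP failure needs a confirmation visit. All of this stands. A reader might infer from the Goldmann paragraph that the primary IOP measure has no protection, and the documents do not support that. What remains is that no sentence requires the operator not to see the value.

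Three other stronger readings also fail:

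- The pneumotonometer text might be taken to hide the arm from the operator. It hides only the reading.
- The second Goldmann reading might be said always to start from the first. The alternating-eyes rule contradicts that unless Table 2's study-eye-only schedule is followed.
- The 4 to 8 points might be read as a share of the 20-point difference in section 7.4. The two are not comparable: one is a single-reading exceedance of one cut point, the other a difference in a 5-year cumulative composite that also includes reoperation, oral CAI and loss of light perception.

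It is also fair to say that the documents neither state that the operator knows the arm nor give a reason for bias in one direction. Section 3 describes both procedures as valid options. The preference for the same operator has a stated purpose, to limit measurement variation, and is a reasonable trade-off. These points limit what can be said about size; they do not close the gap in the procedure.

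**Conclusion.** The point holds as a partial gap. In the default instrument, the person who sets the IOP value is not stated to be masked to treatment and is not explicitly kept from seeing that value, and no rule resets the dial. This falls short of the aim in section 7.3 and leaves a route for bias into one of the four primary failure criteria.

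The size of any bias cannot be derived from the documents. The illustrative increases of about 4 to 8 points at a single reading, and about 2.4 to 6.5 points after confirmation, rest on an assumed normal distribution, an assumed mean and SD, an assumed shift of 0.5 to 1 mmHg confined to one arm and, for confirmation, an assumed correlation. They show that small shifts matter near a cut point; they do not estimate bias in this trial. The change is worth making because it is cheap and follows a safeguard that the plan already uses elsewhere.

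**What to change.** Add to the Goldmann paragraph of section 10.3.7:

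- The operator does not view the dial scale.
- Before each reading the masked reader resets the dial to one fixed value, and reads it after the operator signals that the endpoint is reached.

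Add for all three instruments:

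- No value is disclosed to the operator until all readings of that visit, including a third where needed, are recorded. The reader can say that a third reading is required without giving the values.

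It would also help to say whether the alternating-eyes sequence applies at follow-up, given Table 2.

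The cost is a few sentences, brief site training and a few seconds per reading. Both people are already required, so no staff are added. An operator who knows the arm would still judge the endpoint, so the change does not remove all scope for bias, but that operator could no longer see how close the reading is to a cut point.

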10.3.8. Ultrasonic Pachymetry

CCT measurements will be obtained by Ultrasonic Pachymetry 5 times for each eye. The median of the 5 measurements will be used as the CCT.

10.3.9. Ophthalmoscopy

Any vitreous or retinal abnormalities will be noted and graded as clinically significant or not clinically significant. A vertical cup-to-disc ratio will be measured with a slit lamp lens.

If a dilated exam has been performed within 1 month prior to Screening/Baseline visit, the information collected from that visit may be used for the study.

If there is no view of the posterior chamber, "inadequate view" will be marked on the data collection form.

10.3.10. Optical Coherence Tomography (OCT)

OCT of the macula should be performed at the Screening/Baseline and Month 12 visits to assess for presence or absence of macular edema. Sites will be asked for the central macular thickness at Screening/Baseline and future visits requiring OCT if a participant presents with a decrease in visual acuity of more than 2 lines and macular edema is suspected. Sites will provide a deidentified copy of the macular thickness map to the DCC when performed.

10.3.11. Universal Pain Scale

Following the initial study treatment, participant pain or discomfort will be assessed at Week 1 and Month 1 visits with the Universal Pain Scale (Appendix 1).

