4.2. Secondary Aims

The secondary aims are to compare safety (i.e. complications, loss of best-corrected visual acuity [BCVA], and pain) and vision-related quality of life between the two treatments, including:

1. Cumulative incidence of vision-threatening complications at 1, 3, and 5 years after initial study intervention;
2. BCVA at scheduled visits after the 6-month postoperative visit. Changes of BCVA from baseline and the incidence of eyes that have lost more than 2 lines of BCVA will be compared between groups at each visit.
3. Incidence and severity of pain at the 1-week and 1-month postoperative visits.
4. Total number of visits during the first 3 months, first year, and over 5 years.
5. Changes in vision-related quality of life from baseline to 1-, 3-, and 5-year visits, assessed by the NEI VFQ-25.

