10.3.12. Visual Function Questionnaire (VFQ-25)

Participant-reported visual function will be assessed with the National Eye Institute (NEI) Visual Functioning Questionnaire 25 (VFQ-25, see Appendix 2) at Screening/Baseline, Year 1, Year 3, and Year 5 visits. The VFQ-25 will be administered by site study personnel.

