16.3.3. To compare BCVA at visits after the 6-month postoperative visit

Snellen BCVA will be converted to line scale by logMAR. Differences between study groups will be analyzed both cross-sectionally and longitudinally. Either a Student's t-test or a nonparametric Wilcoxon rank sum test will be used for the cross-sectional comparison between groups and a mixed-effect model with repeated measurements will be used to compare two groups over the study period.

The incidence of loss more than 2 lines from baseline to each follow-up visit will be compared with a Fisher exact test.

16.3.4. To compare incidence and severity of pain between groups at the initial 1-week and 1-month postoperative visits.

The incidence and severity of pain at the 1-week and 1-month follow-up visits will be compared with a Fisher exact test and a Student t test (or a Wilcoxon rank sum test), respectively.

16.3.5. To compare the total number of visits during the first three months, during the first year, and during all five years of the study between groups.

[figure not shown]
Differences between study groups in total number of visits during the first three months, during the first year, and during all five years of the study will be compared between study groups on the distributions with either a Student's t-test or a Wilcoxon rank sum test.

The large number of measures used to assess safety and the frequency of interim analyses to monitor safety introduce the problem of multiple comparisons, i.e. some comparisons are statistically significant because of the large number of statistical tests conducted. Analyses that adjust for multiple comparisons will be conducted and both adjusted and unadjusted multiple comparisons will be reported to the Data and Safety Monitoring Committee.

REFERENCES

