- READ CATEGORIES:
- Excellent 1
 - Very Good 2
 - Good 3
 - Fair 4
 - Poor 5

2. At the present time, would you say your eyesight using both eyes (with glasses or contact lenses, if you wear them) is excellent, good, fair, poor, or very poor or are you completely blind?

(Circle One)

- READ CATEGORIES:
- Excellent 1
 - Good 2
 - Fair 3
 - Poor 4
 - Very Poor 5
 - Completely Blind 6

* Skip Question 1 when the VFQ-25 is administered at the same time as the SF-36 or RAND 36-Item Health Survey 1.0

3. How much of the time do you worry about your eyesight?
(Circle One)

- READ CATEGORIES:
- None of the time.....1
 - A little of the time.....2
 - Some of the time.....3
 - Most of the time4
 - All of the time?.....5

4. How much pain or discomfort have you had in and around your eyes
(for example, burning, itching, or aching)? Would you say it is:
(Circle One)

- READ CATEGORIES:
- None1
 - Mild.....2
 - Moderate.....3
 - Severe, or.....4
 - Very severe?.....5

PART 2 - DIFFICULTY WITH ACTIVITIES

The next questions are about how much difficulty, if any, you have doing certain activities wearing your glasses or contact lenses if you use them for that activity.

5. How much difficulty do you have reading ordinary print in newspapers? Would you say you have:
(READ CATEGORIES AS NEEDED)

- (Circle One)
- No difficulty at all.....1
 - A little difficulty.....2
 - Moderate difficulty.....3
 - Extreme difficulty4
 - Stopped doing this because of your eyesight5
 - Stopped doing this for other reasons or not interested in doing this 6

6. How much difficulty do you have doing work or hobbies that require you to see well up close, such as cooking, sewing, fixing things around the house, or using hand tools? Would you say:
 (READ CATEGORIES AS NEEDED)

(Circle One)

- No difficulty at all.....1
- A little difficulty.....2
- Moderate difficulty.....3
- Extreme difficulty4
- Stopped doing this because of your eyesight.....5
- Stopped doing this for other reasons or not interested in doing this 6

7. Because of your eyesight, how much difficulty do you have finding something on a crowded shelf?
 (READ CATEGORIES AS NEEDED)

(Circle One)

- No difficulty at all.....1
- A little difficulty.....2
- Moderate difficulty.....3
- Extreme difficulty4
- Stopped doing this because of your eyesight.....5
- Stopped doing this for other reasons or not interested in doing this 6

8. How much difficulty do you have reading street signs or the names of stores?

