|------------------|-----------------------|------------------------|------------------------|----------------------------|------------------------|

| | | | | | |
|-------------------------------------------------------------------------------|---|---|---|---|---|
| 17. Do you accomplish less than you would like because of your vision? | 1 | 2 | 3 | 4 | 5 |
|-------------------------------------------------------------------------------|---|---|---|---|---|

| | | | | | |
|---------------------------------------------------------------------------------------------------------|---|---|---|---|---|
| 18. Are you limited in how long you can work or do other activities because of your vision?..... | 1 | 2 | 3 | 4 | 5 |
|---------------------------------------------------------------------------------------------------------|---|---|---|---|---|

| | | | | | |
|--------------------------------------------------------------------------------------------------------------------------------------------------------------------------------|---|---|---|---|---|
| 19. How much does pain or discomfort in or around your eyes , for example, burning, itching, or aching, keep you from doing what you'd like to be doing? Would you say: | 1 | 2 | 3 | 4 | 5 |
|--------------------------------------------------------------------------------------------------------------------------------------------------------------------------------|---|---|---|---|---|

For each of the following statements, please tell me if it is definitely true, mostly true, mostly false, or definitely false for you or you are not sure.

(Circle One On Each Line)

| | Definitely True | Mostly True | Not Sure | Mostly False | Definitely False |
|---------------------------------------------------------------------------------------------------------------------------------|--------------------|----------------|-------------|-----------------|---------------------|
| 20. I stay home most of the time because of my eyesight. | 1 | 2 | 3 | 4 | 5 |
| 21. I feel frustrated a lot of the time because of my eyesight..... | 1 | 2 | 3 | 4 | 5 |
| 22. I have much less control over what I do, because of my eyesight..... | 1 | 2 | 3 | 4 | 5 |
| 23. Because of my eyesight, I have to rely too much on what other people tell me... | 1 | 2 | 3 | 4 | 5 |
| 24. I need a lot of help from others because of my eyesight..... | 1 | 2 | 3 | 4 | 5 |

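### The Week 1 and Month 1 pain comparison is unadjusted although baseline ocular pain is already collected, and its *incidence* means pain present at the visit

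*Combined protocol and SAP*

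**What the plan says.** All references are to the combined protocol and SAP.

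- **Aim.** Section 4.2 lists, among the safety comparisons, "Incidence and severity of pain at the 1-week and 1-month postoperative visits".
- **Measurement.** Section 10.3.11 states that, after the initial treatment, "participant pain or discomfort will be assessed at Week 1 and Month 1 visits with the Universal Pain Scale". Table 2 agrees: the pain-scale row is marked at Week 1 and Month 1 only, and its Screening/Baseline cell is empty.
- **Analysis.** Under Section 16.3.4, incidence and severity "will be compared with a Fisher exact test and a Student t test (or a Wilcoxon rank sum test), respectively". No covariate is named and incidence is not defined.
- **Baseline data on ocular pain.** Section 10.3.12 schedules the VFQ-25 "at Screening/Baseline, Year 1, Year 3, and Year 5 visits". Item 4 (Appendix 2) asks "How much pain or discomfort have you had in and around your eyes", with five levels from none to very severe. Item 19 asks how much such pain, "for example, burning, itching, or aching, keep you from doing what you'd like to be doing". Section 16.3.4 refers to neither.
- **Eligibility.** Section 6.2 does not exclude people whose eye already hurts.

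**The concern.** Participants have uncontrolled glaucoma and an existing shunt, and some may have ocular pain before treatment. If pain before treatment predicts pain after it, part of the spread in Week 1 and Month 1 severity was there beforehand. An unadjusted t test or Wilcoxon test leaves that spread in the error term. The trial pays for the baseline VFQ-25 and then does not use it where it could sharpen a named safety comparison.

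The second issue is wording. With no pain-scale reading before treatment and no restriction on who is counted, the Fisher test compares the proportions with pain at each visit. A reader of the results may take *incidence* to mean pain that began after the procedure. At stake are the precision and the labelling of one secondary outcome.

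**Working it through.** **1. The plan's own figures.** The documents give no sample size, expected rate or standard deviation for pain. The only sizing (Section 7.4) is for 5-year failure, 50% versus 30%. It reproduces: (1.960 + 0.842)² × (0.25 + 0.21) / 0.20² = 90.3, so 91 per group, and 182 / 0.65 = 280. Two-sided 5% is assumed, since sidedness is not stated. None of this is disputed. It supplies only the number treated early on: 280 / 2 = 140 per group, assuming equal allocation and little loss by Month 1.

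**2. Severity: what adjustment could recover.** In a linear ANCOVA with one baseline covariate correlated r with the outcome:

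- residual variance = (1 − r²) × unadjusted variance
- equivalent sample size = n / (1 − r²)
- detectable difference at 80% power = (1.960 + 0.842) × √(2/n) × √(1 − r²), in SD units

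Unadjusted with n = 140: 2.802 × √(2/140) = 0.335 SD.

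| assumed r | variance cut (r²) | gain in n, 1/(1 − r²) − 1 | equivalent n per group | detectable difference (SD) |
|---|---|---|---|---|
| 0.1 | 1% | 1% | 141 | 0.333 |
| 0.2 | 4% | 4% | 146 | 0.328 |
| 0.3 | 9% | 10% | 154 | 0.319 |
| 0.4 | 16% | 19% | 167 | 0.307 |
| 0.5 | 25% | 33% | 187 | 0.290 |
| 0.6 | 36% | 56% | 219 | 0.268 |

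Power at a true difference of 0.335 SD rises from 80% to 84% at r = 0.3, 90% at r = 0.5 and 94% at r = 0.6. At r = 0.1 it stays at 80%. Every r here is an assumption.

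**3. Where r is likely to lie.** Three features of the plan push it down:

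- Items 4 and 19 ask about the eyes together, not the study eye, and use a different response format from the pain scale.
- Treatment may follow the baseline visit by up to 45 days (Section 8.1).
- The Month 1 visit may fall as late as day 59 (Table 1).

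Pain caused by the procedure itself would lower r further.

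**4. What the Fisher test compares.** Let q be the proportion with new pain among those pain-free beforehand, and b the proportion whose earlier pain persists, equal in both groups. The proportion with pain at the visit is b + (1 − b)q. To illustrate, assume q = 40% versus 20%:

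- b = 10%: 46% versus 28%, a difference of 18 points
- b = 40%: 64% versus 52%, a difference of 12 points

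The difference in new-onset pain is 20 points throughout. The documents give neither b nor q. The example shows only that pain at the visit and new-onset pain are different quantities, so the label matters. The r² formula in step 2 does not apply to this comparison.

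**The case against.** The strongest reply is that the plan compares exactly what it sets out to compare. The aim concerns pain at two postoperative visits, with no mention of onset or change. Where change is meant, the same list says so: "Changes of BCVA from baseline and the incidence of eyes that have lost more than 2 lines of BCVA will be compared". Asking how often and how badly people hurt after each procedure is a sensible safety question. This stands. A reader might infer that the plan answers a different question from its aim, or that it wrongly counts old pain as new. The documents do not support that. What remains is an undefined word, used in the BCVA aim for a loss since baseline and in the pain aim with no baseline at all.

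A reader might also infer bias. Earlier pain is balanced between groups in expectation, so the unadjusted tests remain valid.

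Nor are the VFQ-25 pain items ignored altogether. Section 16.3.1 analyses the questionnaire and its subscales. The omission is confined to 16.3.4.

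Two limits on the remedy also stand. The gain could be close to nothing if r is low. And because items 4 and 19 do not identify the eye, incidence among *eyes* without baseline pain cannot be derived from them: discomfort in the fellow eye would exclude a participant whose study eye is pain-free. The items can serve as a covariate, or to define a subset of participants, but not for a change score.

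The pain scale in Appendix 1 is not reproduced in the text available, so its wording and recall period could not be checked. That is not held against the plan.

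**Conclusion.** The point holds as a minor, optional improvement. Section 16.3.4 leaves unused a baseline measure that the trial already collects, so the severity comparison is valid but less precise than it could be. For assumed correlations of 0.1 to 0.6, the cut in residual variance is 1% to 36%, equivalent to about 1% to 56% more participants for severity. The lower part of that range is plausible. The figures apply to linear ANCOVA of severity and to nothing else. Separately, *incidence* in this section means the proportion with pain at the visit and should be called that. Pain is a secondary outcome with no sizing of its own, and the primary comparison is untouched.

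**What to change.** In Section 16.3.4:

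1. Analyse Week 1 and Month 1 severity by ANCOVA adjusted for the baseline VFQ-25 ocular-pain subscale, taken here as items 4 and 19. State the scoring. As printed in Appendix 2 the codes run in opposite directions (higher is worse on item 4, better on item 19), so one must be reversed before they are combined.
2. Keep the unadjusted t or Wilcoxon tests as supportive.
3. Label the Fisher comparison as the proportion of participants with pain at the visit.
4. As a sensitivity analysis, report pain at the visit among participants (not eyes) who answer none to item 4 at baseline.

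Optionally, for participants not yet enrolled, give the pain scale for the study eye at the existing Screening/Baseline visit. That would be a closer covariate and would allow an eye-level statement about new pain.

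Items 1 to 4 cost only SAP wording and use data already scheduled. The optional item adds one short assessment to an existing visit and one mark in Table 2.
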